RESEARCH PROTOCOL

Feasibility of Unattended Home Polysomnography and Comparison to In-laboratory Polysomnography in Pediatric Patients

[name]
Assistant Professor, Otolaryngology
[contact]

[name]
Professor, Pediatrics
Division of Pediatric Allergy, Immunology and Pulmonary Medicine
Director, Sleep Laboratory, St. Louis Children's Hospital
[contact]

[name]., RPSGT, RST
Coordinator Sleep Lab, St. Louis Children's Hospital
[contact]

[name], PhD
Faculty Instructor, Pediatric Anesthesiology
[contact]

Version 1.2
April, 18, 2019
NCT03473548

SYNOPSIS

Study Title	Feasibility of Unattended Home Polysomnography and Comparison to In-laboratory Polysomnography in Pediatric Patients
Objectives	1) To assess the feasibility of unmonitored polysomnography and 2) to compare apnea hypopnea index (AHI), average SPO ₂ , and SPO ₂ nadir between unmonitored polysomnography and in-laboratory polysomnography in pediatric patients.
Study Period	2 years
Number of Subjects	100 children, ages 5 to 12 years of age
Study Design	Single-center, un-blinded, feasibility, methods comparison, and non-inferiority study
Inclusion and Exclusion Criteria	
Inclusion Criteria
 
 a) 5- to 12-years-old b) Parental informed consent c) Suspected Sleep Disordered Breathing 
Exclusion Criteria
 
 a) Developmental delay b) Use of home oxygen c) History of Parasomnia (e.g. narcolepsy, restless leg syndrome, somnambulism) d) History of tracheal surgery e) History of tracheal stenosis f) History of Nocturnal Hypoventilation g) History of Central Sleep Apnea h) Use of a Ventilatory Assist Device (e.g. Non-Invasive Positive Pressure Ventilation)
Measurements	An unattended at-home overnight sleep study using a Type III portable monitor (polysomnography) will be performed on all subjects. All subjects will also have an inpatient, Type I monitored polysomnography performed in the St. Louis Children's Hospital Sleep Laboratory. For both studies the Apnea-Hypopnea Index, Average SPO ₂ , and SPO ₂ nadir will be determined.
Outcomes	Primary outcome will be the feasibility of obtaining greater than or equal to 6 hours of data adequate for polysomnography analysis and determination of an apnea hypopnea index (AHI), average SPO ₂ , and SPO ₂ nadir using un-attended polysomnography. Secondary outcomes will be the comparison of AHI, average SPO ₂ , and SPO ₂ nadir between unattended and inpatient polysomnography. An exploratory outcome will be a comparison of the McGill Oximetry Score between unattended and inpatient polysomnography.

1. Background and Rationale: Childhood obstructive sleep apnea (OSA), defined by periodic, partial or complete obstruction of the upper airway during sleep, is a common disorder in pediatric patients. The prevalence of OSA in children is as high as 5%, and if untreated, OSA can result in significant deleterious behavioral, cognitive, and cardiovascular consequences ¹. First line treatment for pediatric OSA is tonsillectomy and adenoidectomy. This surgery is estimated to be curative in approximately 60% of patients, and even in patients where a complete cure is not achieved there is a significant reduction in symptoms in most cases ². Given the high prevalence and excellent treatment options, it is important that if OSA is suspected a diagnosis is made accurately and efficiently.

The current gold standard for the diagnosis of OSA is in-laboratory polysomnography (PSG), otherwise known as a Type I sleep study. However, in-laboratory PSG is expensive and time consuming as tests are administered by individuals specially trained in sleep medicine in an outpatient setting, and include seven or more channels to monitor sleep, cardiovascular parameters, oximetry, patient position, respiratory effort, and breathing. Furthermore, due to regional variations in sleep center locations, patients do not uniformly have access to centers that perform in-laboratory PSGs. Thus, there has been considerable interest in developing and validating methods to perform home sleep apnea testing, also known as portable monitoring. Indeed, the American Academy of Sleep Medicine (AASM) has recommended the use of portable monitoring as an alternative to in-laboratory PSG for the diagnosis of OSA in selected adult patients ³.

Type II studies are similar to Type I studies except they are not attended by a specially trained individual and can be administered in a subject's home. Type III portable monitoring uses fewer channels (generally 4 to 7) to obtain data than does in-laboratory PSGs, and does not usually have a registered sleep technologist present during the study. In certain circumstances this may reduce the fidelity of the data collected. However, portable monitoring has several advantages over in-laboratory PSGs, including reduced cost, increased patient accessibility, and critically, the ability to assess a more typical night's sleep, since the subject is sleeping in their own home instead of an unfamiliar sleep laboratory. However, while approved for adults, the latest guidelines on childhood OSA published by the American Academy of Pediatrics in 2012 concluded that there is insufficient data in children to either support or refute the utility of portable monitoring in the diagnosis of pediatric OSA ^{4,5}. Several studies have demonstrated the feasibility of both Type II and Type III portable monitoring in children across multiple age ranges ^{1,4-6}, however direct comparison between portable monitoring and in-laboratory attended PSG in children is limited ^{1,6}, and to quote the 2012 guidelines, "... *additional studies of ambulatory PSG in children of varying ages are needed.*" In addition, continued technological advances in sleep monitor design has decreased the size of commercially available sleep monitors to the point that some are now size-appropriate for pediatric patients.

The purpose of the study proposed below is twofold. First we will test the feasibility of conducting portable sleep monitoring in school aged children using the Clevemed Sleepview (www.clevemed.com), one of the smallest portable sleep monitors commercially available at 57 grams. Second we will perform a direct comparison between the results obtained with this portable sleep monitor and those obtained from a standard-of-care in-laboratory attended sleep study performed at the St. Louis Children's Hospital Pediatric Sleep Center. These comparisons will be offered to the families of school age children suspected of having sleep disordered breathing who present to the Washington University Pediatric Otolaryngology Department. We hypothesize that in-laboratory attended polysomnography and portable monitoring will yield similar results in the diagnosis of sleep disordered breathing in school aged pediatric patients. These initial comparisons will be conducted in otherwise healthy children. Future studies will expand this comparison to children with underlying comorbidities, including younger children and those with developmental delay.

2. Enrollment: Patients and their families who present to the Washington University Department of Pediatric Otolaryngology with a suspected diagnosis of sleep disordered breathing will be given information regarding the study in the otolaryngologist's office. A member of the research team will approach the patient and their family once they are identified as needing an in-laboratory sleep study as part of their work up for sleep disordered breathing. Written informed consent will be obtained from the patient's family and assent will be obtained from the patient at that time. The study group will consist of one hundred patients who require diagnostic PSG for sleep disordered breathing. Inclusion and exclusion criteria are based on independent risk factors for respiratory complications following tonsillectomy and adenoidectomy ⁷. The Washington University Pediatric Otolaryngology clinic sees approximately 100 patients a month with tonsillar hypertrophy, snoring, or other concerns for sleep disordered breathing that would warrant a sleep study; the St. Louis Children's Hospital Sleep Laboratory performs approximately 1300 Type I sleep studies a year. We plan to enroll 125 patients in this study, assuming a 20% drop out rate from the study, with an end goal of one hundred study patients. Given the frequency with which patients present with concern for sleep disordered breathing this should be accomplishable in the planned time frame.

3. Eligibility:

3.1. Inclusion Criteria

- 3.1.1. 5- to 12-years-old
- 3.1.2. Parental informed consent
- 3.1.3. Suspected Sleep Disordered Breathing

3.2. Exclusion Criteria

- 3.2.1. Developmental delay
- 3.2.2. Use of home oxygen
- 3.2.3. History of Parasomnia (e.g. narcolepsy, restless leg syndrome, somnambulism)
- 3.2.4. History of tracheal surgery
- 3.2.5. History of tracheal stenosis
- 3.2.6. History of Nocturnal Hypoventilation
- 3.2.7. History of Central Sleep Apnea
- 3.2.8. Use of a Ventilatory Assistant Device

4. Methods:

4.1. Study design: Single-center, un-blinded, feasibility, and methods comparison study

4.2. Otolaryngology Clinic Assessment: Subjects will be identified from patients presenting to the Washington University in St. Louis Pediatric Otolaryngology Clinic who are suspected of having sleep disordered breathing. Subjects who are identified by an attending otolaryngologist as requiring polysomnography as part of their work up will then be approached by a member of the research team who will explain the study to the subject and their family and obtain informed consent. During this visit, subjects will also be administered a short, validated sleep questionnaire, the Modified STOP-Bang Tool for Stratifying OSA Risk in Adolescent Children ⁹. This questionnaire is 8 questions and routinely administered in the Washington University Pediatric Otolaryngology offices.

4.3.1. Unattended Polysomnography: All eligible subjects will be asked to conduct an unattended, overnight sleep study performed in their home prior to in-laboratory polysomnography, using a standard Type III portable monitor. This study will be performed with

an FDA approved sleep monitor (e.g CleveMed SleepView or similar). Per American Academy of Sleep Medicine (AASM) guidelines, portable sleep monitoring will include air flow, respiratory effort, heart rate and blood oxygenation. Airflow will be measured using a nasal cannula and pressure transducer which is located within the home sleep test (HST) recording device. Respiratory effort will be recorded using Respiratory Inductance Plethysmography (RIP) belts that will go around the chest at the nipple line and around the abdomen at the navel level. Blood oxygenation and heart rate will be recorded by pulse oximetry that will be placed on one finger. Each study participant and their family will be shown and educated on how to apply each of the sensors by a member of the study team. Unattended sleep studies will be interpreted by an individual trained in sleep medicine. The first assessment of the Unattended sleep study for each individual patient will be readability of the recordings.

Polysomnography testing will determine the apnea hypopnea index (AHI), blood saturation oxygen nadir (SPO₂ nadir), and average blood oxygen saturation ³. The AHI is defined as the average number of hypopneas (episodes of decreased breathing) and apneas (episodes of cessation of breathing) per hour of sleep. Apneas and hypopneas will be defined per the American Academy of Sleep Medicine manual for scoring sleep and associated events ¹⁰. The objective is to obtain greater than or equal to 6 hours of data adequate for polysomnography analysis and determination of an apnea hypopnea index (AHI), average SPO₂, and SPO₂ nadir using home un-attended polysomnography.

A McGill Oximetry Score ¹¹, which only uses the frequency and depth of SPO₂ desaturations throughout a night's sleep to assign a score of 1 (normal/inconclusive), 2 (mildly abnormal), 3 (markedly abnormal), and 4 (severely abnormal) will be also be assigned to each home sleep test.

Fidelity of data collection using at home sleep studies is reliable, but not 100% reliable ³. For example, subjects may unconsciously remove the nasal cannula or the finger pulse oximeter in their sleep, resulting in data drop outs. A subject's parent or guardian will be requested to periodically monitor the subject throughout the night and be instructed on how to reapply sensors to minimize data drop outs. Should data from an initial sleep study be uninterpretable based on sleep study expert opinion we will ask the subjects to attempt the unattended sleep study an additional time. A recent study on the feasibility of Type II comprehensive (i.e. greater than 7 channel) pediatric sleep studies, reported that 91% of home sleep studies are successful on initial attempt and a total of 98% are successful after one repeat testing ¹². A 2013 assessment of Type III sleep studies performed both in a hospital setting (26 patients) and at home (75 patients) found that technically acceptable and interpretable studies were obtained from 93% of subjects ¹³.

Should data from the second sleep study be uninterpretable we will not proceed with further testing of these subjects by home sleep study. Regardless of whether a subject successful completes home sleep testing, in-laboratory polysomnography will still be performed as part of their work up for sleep disordered breathing.

4.3.2. Parental Monitoring Plan for Unattended Polysomnography: Parents will be instructed that while the device is FDA approved for use in adults it is not FDA approved in children and therefore they will need to monitor their child more closely during the night than they would have to during a typical night's sleep. Parents should remain in close enough proximity to hear their child should their child call out for them during the night for assistance with any aspect of the device. Parents will be instructed that improper routing of leads may result in a choking hazard. Parents will be instructed to inspect for proper effort belt, nasal cannula, and pulse oximeter placement at least every two hours. Parents will be instructed that should they ever feel the device presents a significant choking hazard to their child they should entirely remove the device and stop the study.

4.4. In-laboratory Polysomnography: All eligible subjects will have in-laboratory polysomnography as is routinely performed in the diagnostic work up for suspected sleep disordered breathing. The in-laboratory sleep study will be done at the St. Louis Children's Hospital Pediatric Sleep Center, which is an American Academy of Sleep Medicine accredited sleep disorder center. The Center is sound-proof, and has been designed to provide as natural and home-like an atmosphere as possible. Infrared monitoring equipment allows for patient observation from outside of the patient's sleep room. At least one parent is required to stay in the room overnight with the patient. A second parent can stay as well, but not required. The Center is located inside of St. Louis Children's Hospital within an inpatient medical unit, which is staffed with physicians and nurses 24 hours per day.

Per American Academy of Sleep Medicine (AASM) guidelines, in-laboratory sleep monitoring is attended by a specially trained technologist who sets up the sleep study, observes the subject throughout the duration of the sleep study, and is available to troubleshoot in real time any monitoring issues that may arise. In-laboratory polysomnography consists of 21 leads that measure electroencephalogram, electrocardiogram, air flow, respiratory effort, heart rate, activity, and blood oxygenation monitoring. In-laboratory sleep studies are scored by a trained Registered Polysomnographic Technologist or Registered Sleep Technologist and interpreted by a physician. Polysomnography testing will determine the sleep stages, apnea hypopnea index (AHI), blood saturation oxygen nadir (SPO₂ nadir), and average blood oxygen saturation, as defined above ³. A McGill Oximetry Score will also be calculated for the in-laboratory PSG.

4.6. Subject assessments: The unattended home polysomnogram will record blood oxygen concentration, pulse rate, respiratory effort, air flow and respiratory effort. The in-laboratory polysomnogram will record these parameters and will also measure electroencephalography, electrocardiogram, and heart rate.

4.7. Conclusion of study: The study ends with the completion of the in-laboratory polysomnogram. Additionally, the study ends at any time the patient or parent/caregiver requests it to end. Appropriate treatment for any diagnosis of sleep disordered breathing will proceed based on the attending otolaryngologist recommendations. Recommendations and treatment will not be affected by participation in the investigation. As home sleep testing in pediatric patients is exploratory; only the in-laboratory sleep study will be used in making any diagnosis of sleep disordered breathing and in determining treatment options.

5. Data Collection and Monitoring

5.1. Clinical Assessments: At the completion of both the unattended and in-laboratory polysomnography we will determine an Apnea-Hypopnea Index, Average SPO₂, and SPO₂ nadir for each subject. An assessment of the technical quality of each study will be made. The in-laboratory polysomnogram will be scored and interpreted via standard practice for the St. Louis Children's Hospital Pediatric Sleep Center and included in the patient's medical record. The unattended polysomnogram will not be included in the patient's medical record and will only be accessible to study team members.

6. Outcome Measures

7.1. Primary Outcome Measure: The feasibility of obtaining greater than or equal to 6 hours of data adequate for polysomnography analysis and determination of an apnea hypopnea index (AHI), average SPO₂, and SPO₂ nadir using home un-attended polysomnography.

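### Nothing masks the home-study reader to the laboratory result or makes the home AHI and diagnosis final before it, so agreement on these two secondary outcomes may be inflated

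*Protocol*

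**What the plan says.** The synopsis gives the design as "Single-center, un-blinded, feasibility, methods comparison, and non-inferiority study" and section 4.1 as "Single-center, un-blinded, feasibility, and methods comparison study". Neither says whom un-blinded covers.

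Section 4.3.1 has the home study "performed in their home prior to in-laboratory polysomnography". On reading, it says: "Unattended sleep studies will be interpreted by an individual trained in sleep medicine". It adds: "The first assessment of the Unattended sleep study for each individual patient will be readability of the recordings". Apneas and hypopneas follow the AASM scoring manual. Whether a recording is interpretable, and so whether the home study is repeated, is left to expert opinion.

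Section 4.4 has a registered technologist score the laboratory study and a physician interpret it. Section 5.1 says that AHI, average SpO2 and SpO2 nadir are determined once both studies are complete, in words that fit either each study in turn or the pair. The laboratory study goes into the medical record. The home study stays out of it and is open only to the study team. Section 7.3 has home reports coded, with the link to names kept separately.

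AHI (6.2.1) and diagnosis (6.2.4) are compared between methods, and 6.4 plans Bland-Altman analysis. The hypothesis in section 1 is that "in-laboratory attended polysomnography and portable monitoring will yield similar results in the diagnosis of sleep disordered breathing".

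**The concern.** A methods comparison rests on two readings made independently. If the person who settles the home AHI knows the laboratory AHI, doubtful events can be resolved toward it without any intent to do so. The home reading leaves some room for this. The protocol expects sensor drop-outs and relies on expert opinion for interpretability, and the home channels it lists do not include EEG.

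The pull would be toward agreement, which is the direction of the stated hypothesis. It would narrow the Bland-Altman limits for AHI and raise concordance of diagnosis. A reader of the results could not tell real agreement between devices from agreement created in the reading. Direct comparison with the laboratory study is the second of the two purposes given in section 1, so this matters even though the outcomes are secondary.

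Who may know what, and when a reading becomes final, are conduct rules. They have to be in force when the recordings are read.

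**Working it through.** **The plan's own figure.** Section 2 plans 125 enrolled, with 20% drop-out, for 100 study patients: 100 / (1 − 0.20) = 125. This reproduces. The point does not depend on it, except that 100 completers means at most 100 home-laboratory pairs.

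**What each provision does for the home reading.**

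| Provision | Effect on the home reader |
|---|---|
| Un-blinded label (synopsis, 4.1) | No exception for readers; may be meant for participants only |
| Home study first (4.3.1) | Orders the recordings, not the readings |
| Readability judged first (4.3.1) | Suggests an early look; sets no deadline for AHI or diagnosis |
| Timing in 5.1 | After each or after both; neither sense locks the home result |
| Laboratory study in the medical record (5.1) | No bar on the home reader's access |
| Home study kept out of the record (4.7, 5.1, 7.3) | Protects the laboratory reading and care, not the home reading |
| Coded home reports (7.3) | A reader working only from the code would need the link; reading under the code is not required |
| AASM definitions (4.3.1) | Limit discretion; how much is left is not shown |

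Following the text as written, a home AHI settled after the laboratory result is known would be no deviation.

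**Reach.** Event-scored secondary outcomes are 6.2.1 and 6.2.4, 2 of 4. The other two (6.2.2, 6.2.3) and the exploratory McGill score are read from oximetry, and the protocol does not show that they leave similar room for judgement. The single primary outcome, at least 6 hours of usable home data, is not an agreement measure.

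**Direction.** Let d be home minus laboratory. If the home value is moved a fraction f toward the laboratory value, d becomes (1 − f)d, so the mean bias and the limits (mean ± 1.96 SD) are multiplied by (1 − f). With the same f for every child, the paired t statistic (mean divided by SD/√n) and the Wilcoxon ranks do not change. Uneven shrinkage would change them somewhat. In neither case are these tests designed to detect the problem.

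**Illustration on assumed inputs.** None of these comes from the protocol: a log-AHI-like score, between-child SD 1, independent error SD 0.5 for each method, diagnosis cut at the median. Then SD(d) = √(0.5² + 0.5²) = 0.707 and the half-width of the limits is 1.96 × 0.707 × (1 − f). With a median cut, kappa = (2/π) × arcsin(ρ), where ρ is the correlation of the two readings (0.80, 0.835, 0.884 and 0.949 for the four rows).

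| f | Half-width | Kappa |
|---|---|---|
| 0 | 1.39 | 0.59 |
| 0.10 | 1.25 | 0.63 |
| 0.25 | 1.04 | 0.69 |
| 0.50 | 0.69 | 0.80 |

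The table shows direction only. The protocol gives no basis for any value of f.

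**The case against.** The strongest reply is that this is an omission and that the planned order already favours an early home reading. The home study comes first, an expert must open it to judge whether it is readable and whether to repeat it, and the study ends with the laboratory night. Un-blinded may simply describe families, and reading procedures may sit in a document not shown. Much of this stands: the label is not itself an error, and exposure is not shown to be the default. It does not close the gap, because an early readability check does not make the AHI or diagnosis final, and the one timing statement, in 5.1, allows a later determination.

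Several stronger readings are tempting and are not supported:

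- *That readers will see both results, or that one team scores both studies.* The title page lists roles that include "Director, Sleep Laboratory" and "Coordinator Sleep Lab", and 5.1 speaks generically in the first person plural. But 4.4 and 5.1 assign the laboratory study to a technologist, a physician and the centre's standard practice, and the protocol does not say who scores which study.
- *That the laboratory reading is equally exposed.* Home results stay out of the record and only the laboratory study may be used for diagnosis. This route is a lesser risk, though not fully closed, because study team members have access to home results.
- *That the damage could not be undone.* Masked re-scoring of stored home recordings could restore independence if they are kept.
- *That a known number of pairs is affected.* The 85% feasibility threshold and the cited success rates do not bound the number of usable pairs, and nothing says how many would be read with the laboratory result known.

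**Conclusion.** The concern holds in a limited form. The protocol permits the home AHI and diagnosis to be settled with the laboratory result known, and nothing in it masks the home reader or fixes when those readings are final. If that happens, agreement on 2 of 4 secondary outcomes may be inflated toward the hypothesis. Only the direction can be stated; the size is unknown.

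The conclusion assumes that some discretion remains after the AASM definitions are applied and that the laboratory result is within the home reader's reach. Both are plausible from the text, and neither is proved by it. The primary feasibility outcome is not touched by this route, and neither is clinical care. Confidence is medium. The change should be made because it is cheap and secures the independence that the comparison needs.

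**What to change.** In the synopsis and 4.1, state that un-blinded applies to participants and families and not to the home-study reader.

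In 4.3.1 and 5.1, replace the ambiguous timing with one rule: the home AHI and diagnosis are scored and locked with a date, under the study ID and without access to the laboratory result, preferably before that result is available. Any home reading made with the laboratory result known is recorded as such.

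The cost is a lock step and some scheduling of existing readers. The study codes in 7.3 and the home-first order already make it workable. No separate laboratory reader and no added patient procedure are needed.
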